6. GENERAL STATISTICAL CONSIDERATIONS

6.1. General Principles

Tabulations will be used extensively to summarize the data. Unless otherwise specified, all continuous variables will be summarized using the following descriptive statistics: n (number of non-missing observations for the measure being summarized in the specified analysis population), mean, standard deviation, median, maximum and minimum. Immunogenicity summaries will use geometric mean. The frequency and percentages (based on the sample size for the specified analysis population and treatment group, N) of observed levels will be reported for all categorical measures. Wilson confidence intervals for binomial proportions and differences in binomial proportions will be computed for efficacy variables. Blaker confidence intervals for binomial proportions and differences in binomial proportions will be computed for safety variables. In general, all data will be listed by treatment group and/or subject, and when appropriate by visit number within subject.

All summary tables will be structured with a column/sub-table for each treatment group (Vaccine, Placebo, and All Subjects). The total population size (N) relevant to that table/column if applicable, including any missing observations will be displayed in the tables.

Note that in the data listings, Subject ID is the unique subject identifier, not the Study ID used on study and dates will not be included, only Study Day.

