6.1.1. Pseudo Code

The following SAS® pseudo code will be used to calculate the following for safety analyses:

Chi-Square test at 5% two-sided significance level:

```
proc freq;
    Table treatment*analysis_variable / chisq;
    ods output ChiSq=outputdsn;
run;
```

Fisher's Exact test at 5% two-sided significance level:

```
proc freq;
    Table treatment*analysis_variable / exact;
    ods output FishersExact=outputdsn;
run;
```

95% Wilson CI for proportions/percents:

```
Proc freq;
    Table treatment*analysisvariable / binomial(wilson);
    ods output binomialcls=outputdsn;
Run;
```

95% Wilson CI for difference in proportions (produces Newcombe CI):

```
Proc freq;
    Table treatment*analysisvariable / riskdiff(cl=Wilson);
    Exact Riskdiff;
    ods output pdiffcls=outputdsn;
Run;
```

95% Exact Blaker CI for proportions/percents:

```
Proc freq;
  Table treatment*analysisvariable / binomial(blaker);
  ods output binomialcls=outputdsn;
Run;
```

Odds ratios using ordinal logistic regression:

```
PROC LOGISTIC data=dataset;
  Class treatment (ref='Placebo') baseline(ref='None') / param=reference;
  Model severity_postvaca1=baseline treatment;
Run;
```

```
PROC LOGISTIC data=dataset;
  Class treatment (ref='Placebo') baseline(ref='None') / param=reference;
  Model severity_postvac2=baseline treatment;
Run;
```

See Section 8 for pseudocode to be used in the efficacy analyses.

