Ods output parameterestimates=ests(keep=HazardRatio HRUpperCL HRLowerCL);
run;
```

The p-value from the score test of the treatment main effect will be calculated and presented. Results of this sensitivity analysis will be provided in [Table 8](#).

Finally, a sensitivity analysis will be performed, in which subjects who develop HCV infection and do not go on to develop chronic infection will be treated as experiencing a competing risk in the Fine-Gray proportional hazards regression model.

Both the stratified and unstratified with interaction terms models will be fit.

```
proc phreg data=dataset;
class treatment / order=internal ref=first param=glm;
model time*status(0) = treatment / eventcode=1;
hazardratio treatment / diff=pairwise;
```

```

strata gender il28bstatus;
Ods output parameterestimates=ests(keep=HazardRatio HRUpperCL HRLowerCL);
run;

proc phreg data=dataset;
class treatment / order=internal ref=first param=glm;
model time*status(0) = treatment gender|time il28bstatus|time /
eventcode=1;
hazardratio treatment / diff=pairwise;
Ods output parameterestimates=ests(keep=HazardRatio HRUpperCL HRLowerCL);
run;

```

The same summaries as the mITT analyses will be calculated and presented. Results of this sensitivity analysis will be provided in [Table 8](#) and [Table 9](#).

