8.3. Exploratory Efficacy Analyses

Exploratory Objective 1: To determine if AdCh3NSmut1 and MVA-NSmut HCV vaccines will reduce incidence of incident HCV infection compared to placebo among HCV-uninfected IDU.

Kaplan-Meier curves for incident HCV infection will be generated for both the ATP and mITT populations ([Figure 5](#) and [Figure 6](#)).

The reduction in incident HCV incidence will be calculated from the hazard ratio of a stratified Cox model. The stratification factors that will be used are gender and IL28B status (i.e. there will be four strata: Female & CC, Female & CT/TT, Male & CC, Male & CT/TT). The model to be fit for subject i is:

$$\log h_i(t) = \alpha_j(t) + \beta x_i$$

where $h(t)$ is the hazard function at time t , $\alpha_j(t)$ is the logarithm of the baseline hazard function for strata j , x_i is a binary indicator for membership in the vaccine as compared to the placebo group. See Section 3.3.3 for definition of incident HCV infection.

The model described above will be fit using PROC PHREG following the pseudocode below:

```

proc phreg data=dataset;
class treatment;
model time*status(0) = treatment;
strata gender il28status;
Ods output parameterestimates=ests(keep=HazardRatio HRUpperCL HRLowerCL);
run;

```

Vaccine Efficacy = 1 – Hazardratio;

Lower 95% CI= 1 – HRUpperCL which is the same as 1 – exp(estimate + $\Phi^{-1}(.975)$ *stderratio)

Upper 95% CI= 1 – HRLowerCL which is the same as 1 - exp(estimate – $\Phi^{-1}(.975)$ *stderratio)

The p-value of the score test of the treatment main effect (equivalent to the log-rank test) will be calculated and presented. Analyses will be performed in both ATP and mITT populations. The number of incident HCV infections defined as detection of viremia (RNA Reactive) per treatment group and the vaccine efficacy and associated 95% confidence interval will be summarized by treatment group in [Table 10](#). Stratum-specific summaries will be presented in [Table 11](#).

A sensitivity analysis will also be performed by repeating the above using an interval censored Cox model [12]. The model will be fit using PROC ICPHREG following the pseudocode below:

```
proc icphreg data=dataset;
    class treatment;
model (StartInterval, EndInterval) = treatment;
strata gender il28status;
Ods output parameterestimates=ests(keep=HazardRatio HRUpperCL HRLowerCL);
run;
```

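### The stratified Cox code for incident HCV infection sets no reference level for treatment; run as written, under the usual default and coding, it would report vaccine efficacy as 1 − 1/HR instead of 1 − HR

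*SAP*

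**What the plan says.** SAP Section 8.3, Exploratory Objective 1, gives a stratified Cox model in which "x_i is a binary indicator for membership in the vaccine as compared to the placebo group". The SAP then says: "The model described above will be fit using PROC PHREG following the pseudocode below". The code block has the statement "class treatment" with no options, and the result is turned into efficacy by "Vaccine Efficacy = 1 – Hazardratio". The output data set keeps only the hazard ratio and its two limits.

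Other code in the SAP handles treatment differently:

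- Section 6.1.1, ordinal logistic code (twice): "Class treatment (ref='Placebo') baseline(ref='None') / param=reference".
- Section 8.1, Fine-Gray code (twice): "class treatment / order=internal ref=first param=glm".
- Section 8.1, primary stratified Cox code: no CLASS statement.
- Section 8.3, Objective 1, covariate-adjusted PROC PHREG code: no CLASS statement.
- Section 8.3, Objective 1, both PROC ICPHREG blocks (stratified and covariate-adjusted): a bare CLASS statement again.

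SAP Section 6.1 names the groups Vaccine and Placebo. Section 13 specifies SAS 9.4 or above.

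**The concern.** The formula VE = 1 − HR is right only when the HR is vaccine over placebo. A bare CLASS statement leaves that direction to the software default and to how the variable happens to be coded. If vaccine ends up as the reference, the HR is placebo over vaccine and the efficacy has the wrong sign. The SAP fixes the reference in its logistic and Fine-Gray code, so the gap in Objective 1 looks like an omission and not a convention.

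Objective 1 asks whether vaccination changes acquisition of HCV. Protocol Section 2.4.2 discusses whether an adenovirus-vectored vaccine might raise the risk of HCV infection, and judges it less likely. A reversed sign could suggest that signal where there is none, or mask it where there is one.

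**Working it through.** **No plan figure is in dispute.** The only design figure on the hazard-ratio scale is in SAP Section 5: 43 events for 85% power at HR 0.40. It reproduces: 4 × (1.960 + 1.036)² / (ln 0.40)² = 42.8, rounded up to 43. It refers to chronic infection in the ATP cohort and has no bearing on direction. HR 0.40 appears below only as an example, and no interval is built on 43 events, because Objective 1 counts incident infections.

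**Step 1: which level is the reference.** Assumption, not stated in the documents: PROC PHREG with a bare CLASS statement orders the levels and takes the last as reference.

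| Coding of treatment | Last level | Reference |
|---|---|---|
| Placebo / Vaccine | Vaccine | vaccine |
| 0 = placebo, 1 = vaccine | 1 | vaccine |
| A = vaccine, B = placebo | B | placebo |
| 1 = vaccine, 2 = placebo | 2 | placebo |

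The first two fit the rest of the SAP. Section 6.1.1 refers to a level called Placebo, and the model text describes a vaccine indicator. The fourth fits badly. Without a CLASS statement, the primary code in Section 8.1 would estimate the effect of moving from 1 to 2, which is placebo versus vaccine, and the first-level reference in the Fine-Gray code would be vaccine.

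**Step 2: what the code then returns.** With vaccine as reference, HR(printed) = 1/HR, so VE(printed) = 1 − 1/HR. Each confidence limit is transformed in the same way.

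| True HR (vaccine/placebo) | Intended VE | 1/HR | Printed VE |
|---|---|---|---|
| 0.30 | 70% | 3.33 | −233% |
| 0.40 | 60% | 2.50 | −150% |
| 0.60 | 40% | 1.67 | −67% |
| 0.80 | 20% | 1.25 | −25% |
| 1.25 | −25% | 0.80 | +20% |
| 1.50 | −50% | 0.67 | +33% |

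**Step 3: check by refitting.** One simulated data set (20,000 subjects, four strata, true HR 0.40) was fitted by stratified Cox regression in Python with each reference in turn. Placebo as reference gave HR 0.376 (VE 62%). Vaccine as reference gave HR 2.659 (VE −166%), the reciprocal, with an identical p-value. This confirms the effect of switching the reference. It does not test the SAS default.

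**Step 4: which results use this code.** The stratified PHREG block feeds the stratified Cox rows of Table 10, the stratum rows of Table 11 and the antibody-defined repeats in Tables 12 and 13. The covariate-adjusted PHREG block for the same objective has no CLASS statement. With a 0/1 indicator it gives vaccine over placebo, so Objective 1's main and sensitivity analyses could report opposite signs from the same data.

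**The case against.** The strongest reply is that this is pseudocode under a correct specification. The text fixes the direction of the effect, and the blocks are visibly schematic: the IL28B variable is spelled two ways across Sections 8.1 and 8.3, and the retained output columns omit the estimate and standard error that the confidence-limit lines mention. A programmer must adapt the code and could put the reference right in doing so. That stands, and it makes the inversion conditional. It does not remove the conflict, because the SAP says the model will be fitted following this code.

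The coding of treatment is also not stated. The protocol summary labels vaccine Arm A and placebo Arm B, and under A/B labels the last level is placebo and the HR is correct. That is possible but sits poorly with the reference named in Section 6.1.1.

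Nor would an inversion be well hidden. The Table 10 shell prints infections and denominators by arm beside the efficacy, Figures 5 and 6 show Kaplan-Meier curves, and Table 27 gives infection rates by arm. A careful reader could see the contradiction, although the SAP plans no such check and the unchanged p-value gives no warning.

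A reader might infer that the reported efficacy will certainly be inverted, or that the primary result is at risk. The documents support neither. The first needs a software default and a coding that they do not state. As for the second, the primary Cox code has no CLASS statement and the Fine-Gray code sets its reference explicitly.

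**Conclusion.** The point holds in conditional form. The stratified PHREG code for incident infection does not secure the vaccine-versus-placebo direction that its own text requires. If the last level is the default reference and treatment is coded 0/1 or Placebo/Vaccine, running the code as written gives VE = 1 − 1/HR, and any effect other than HR = 1 changes sign. The score (log-rank) p-value is unaffected.

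The scope is the stratified Cox estimates and intervals for Objective 1. The two PROC ICPHREG blocks share the omission. Their default reference is not stated in the documents and was not checked, so no direction is claimed for them, but they should be corrected together. It would go too far to say that everything in Tables 10 to 13 is inverted, because the covariate-adjusted PHREG summaries for this objective are not exposed. The endpoint is exploratory, so this is a minor code correction.

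**What to change.** In the Objective 1 stratified PHREG block, write `class treatment (ref='Placebo') / param=ref;`. Add `(ref='Placebo')` to the CLASS statement in both ICPHREG blocks. Alternatively, in PHREG only, drop CLASS and use the 0/1 vaccine indicator as in Section 8.1. In either case keep the parameter and level label in the ODS output data set, so that the direction of each hazard ratio can be read from the output.

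The cost is one option per statement and a longer KEEP list. No data, estimand, sample size or p-value changes. It should be done before the programs are run on unblinded data.

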8.2.14 Days 390–570, Visits 19–25

Visit	Target (Day)	Window (Days)
19	390	+ 7
20	420	+ 7
21	450	+ 7
22	480	+ 7
23	510	+ 7
24	540	+ 7
25	570	+ 7

- Current health status will be reviewed and any changes since the last visit will be noted.
- A targeted physical examination may be performed, if indicated, based on review of current health status.
- Behavioral risk will be assessed using an interviewer administered questionnaire at visits 21 and 24.
- Immunosuppressant concomitant medications and medications for the treatment of HCV infection will be recorded.
- SAEs that have occurred since the last contact will be collected.
- Approximately 10 mL of venous blood will be collected for HCV viremia.
- Counseling on avoidance of HCV and HIV infection, and pregnancy will be conducted.
- Referral to drug treatment and needle exchange programs will be provided.

8.2.15 Day 600, Visit 26

(Window: Day 593 to 607)

- Current health status will be reviewed and any changes since the last visit will be noted.
- A targeted physical examination may be performed, if indicated, based on review of current health status.
- Behavioral risk will be assessed using an interviewer administered questionnaire.
- Immunosuppressant concomitant medications and medications for the treatment of HCV infection will be recorded.
- SAEs that have occurred since the last contact will be collected.
- Approximately 23 mL of venous blood will be collected for hematology and biochemistry parameters, as described in Section 7.6.1, and performed by the

local laboratory.

- Approximately 20 mL of venous blood will be collected for anti-HCV, HbsAg, anti-HIV and HCV viremia.
- Approximately 100 mL of venous blood will be collected for immunologic assays.
- Counseling on avoidance of HCV and HIV infection, and pregnancy will be conducted.
- Referral to drug treatment and needle exchange programs will be provided.
- Subjects will be thanked for participating in the study and contact information for end of study results will be confirmed.

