infection, the 6-month chronic infection endpoint will be coded as censored, with time to event defined as the elapsed time from the first (second) vaccination, to six months post completion of follow-up for acute HCV infection (26 months), or to the first occurrence of loss to follow-up or of a criterion listed under the censoring criteria for the mITT (ATP) cohort. For subjects in the mITT (ATP) cohort with acute HCV infection, the 6-month chronic infection endpoint will be coded as an observed event if the 6-month chronic infection endpoint definition is met, and as censored otherwise, with time to event defined as the elapsed time from the first (second) vaccination to the date of the sample collection with available test result nearest to the target assessment date of six months after primary acute infection. Time to event and censoring status for 9-month chronic infection are defined analogously. The reduction in chronic HCV incidence will be calculated from the hazard ratio of a Cox model stratified by gender and IL28B status fit to the time to event data which includes a binary indicator for membership in the vaccine as compared to the placebo arm. A sensitivity analysis will be performed, in which subjects with acute infection who do not go on to develop chronic infection will be treated as experiencing a competing risk in the Fine-Gray proportional hazards regression model.

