3.3.2. Persistent Viremia

For the primary efficacy endpoint, persistent viremia is defined as:

1. The presence of the same virus (as confirmed by HCV core-E1 phylogenetic analysis testing) in blood samples collected at the first visit where HCV RNA is detected (incident infection) provided sufficient sample is available, and a subsequent sample collected at month 6 (not less than 159 or more than 201 days following incident infection); and

2. A third HCV RNA positive sample taken at a time point in between these two samples (incident and month 6).

Note: If there are two or more samples within the 159 to 201 day window for the month 6 collection, the test result from the collection date closest to 180 days after incident infection will be used.

For exploratory endpoint 2, persistent viremia is defined as:

1. The presence of the same virus (as confirmed by HCV core-E1 phylogenetic analysis testing) in blood samples collected at the first visit where HCV RNA is detected (incident infection) provided sufficient sample is available, and a subsequent sample collected at month 9 (not less than 249 or more than 291 days following incident infection); and
2. A third HCV RNA positive sample taken at a time point in between these two samples (incident and month 9).

Note: If there are two or more samples within the 249 to 291 day window for the month 9 collection, the test result from the collection date closest to 270 days after incident infection will be used.

In the scenario in which HCV core-E1 phylogenetic analysis testing cannot be performed on the blood samples collected at the incident infection (e.g. due to low viral load or low amount of sample), HCV core-E1 phylogenetic analysis testing may be performed on a sample from a supplemental visit or the first H-series visit. The earliest observed result among these timepoints will be used to identify the virus at the incident infection.

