The planned duration of the study is approximately 63 months total including accrual time for subjects (assuming 31 months of screening/enrollments, plus 3 months of halted enrollment for the first interim analysis), 2 months vaccination, 18 months follow-up of each enrolled subject, and 9 months extended observation (monthly), from the time of infection, for subjects becoming viremic in the last month of follow-up.

The follow-up period for detection of HCV infection will start after the second injection of vaccine and will last 18 months. Subjects who become viremic will be followed for 9 months after detection of HCV (up to month 29). The trial will be considered closed when the observation period for the last subject that became viremic during the 18 months follow-up is completed. A schematic of the general design is provided in [Figure 1](#). [Table 1](#) and [Table 2](#) presents the schedule of events for each visit for subjects with and without confirmed HCV infection.

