8.1. Primary Efficacy Analysis

For the evaluation of the primary efficacy objective of this study, a time to event analysis will be performed in the ATP cohort as follows:

- For subjects without HCV infection, the 6-month chronic infection endpoint will be coded as censored, with time to event defined as the elapsed time from the second vaccination, to the end of the 26 months follow up, or to the last observed visit before loss to follow-up or to the earliest time any criterion listed under the censoring criteria for the ATP cohort was met.
- For subjects who develop HCV infection, the 6-month chronic infection endpoint will be coded as an observed event if the 6-month chronic infection endpoint definition is met, and as censored otherwise, with time to event (chronic or non-chronic infection) defined as the elapsed time from the second vaccination to the date of the sample collection with available test result nearest to the target assessment date of six months after incident infection.

Kaplan-Meier curves for chronic HCV infection will be generated for both the ATP and mITT populations (Figure 3 and Figure 4).

As the primary analysis of the primary outcome measure, the reduction in chronic HCV incidence will be calculated from the hazard ratio of a stratified Cox model for the ATP population. The stratification factors that will be used are gender and IL28B status (i.e. there will be four strata: Female & CC, Female & CT/TT, Male & CC, Male & CT/TT). The model to be fit for subject i is:

$$\log h_i(t) = \alpha_j(t) + \beta x_i$$

where $h(t)$ is the hazard function at time t , $\alpha_j(t)$ is the logarithm of the baseline hazard function for strata j , x_i is a binary indicator for membership in the vaccine as compared to the placebo group.

The model described above will be fit and estimates of vaccine efficacy ($1 - \text{Hazard Ratio}$) will be obtained using PROC PHREG following the pseudocode below:

```
proc phreg data=dataset;
model time*status(0) = treatment;
strata gender il28status;
Ods output parameterestimates=ests(keep=HazardRatio HRUpperCL HRLowerCL);
run;
```

Vaccine Efficacy = $1 - \text{Hazardratio}$;

Lower 95% CI = $1 - \text{HRUpperCL}$ which is the same as $1 - \exp(\text{estimate} + \Phi^{-1}(.975) * \text{stderrratio})$

Upper 95% CI= 1 – HRLowerCL which is the same as $1 - \exp(\text{estimate} - \Phi^{-1}(.975) * \text{stderrratio})$

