Analyses will be performed in both ATP and mITT populations. The number of incident HCV infections per treatment group and the vaccine efficacy and associated 95% confidence interval will be summarized by treatment group in [Table 10](#).

For both the standard and interval-censored versions of the Cox model, an additional sensitivity analysis will be performed in which the Cox model will be fit with binary indicators for membership in the vaccine as compared to the placebo group, female as compared to male, and CC IL28B status compared to CT/TT. The interaction between time and gender will be assessed using the product of time and the binary indicator for gender as an interaction term in the model. Likewise, the interaction between time and IL28B status will be assessed using the product of time and the binary indicator for gender as an interaction term in the model. The reduction in incident HCV incidence will be calculated from the hazard ratio of this model.

The model described above will be fit using PROC PHREG following the pseudocode below:

```
proc phreg data=dataset;
model time*status(0) = treatment gender|time il28bstatus|time;
Ods output parameterestimates=ests(keep=HazardRatio HRUpperCL HRLowerCL);
run;
```

```
proc icphreg data=dataset;
    class treatment;
model (StartInterval, EndInterval) = treatment gender|time
il28bstatus|time;
Ods output parameterestimates=ests(keep=HazardRatio HRUpperCL HRLowerCL);
run;
```

These additional sensitivity analyses will be performed in both ATP and mITT populations. Summaries will be provided in [Table 11](#).

The above analyses will be repeated using the secondary definition of incident HCV infection (See Section 3.3.3). The summaries will be presented in [Table 12](#) and [Table 13](#).

Exploratory Objective 2: To determine if AdCh3NSmut1 and MVA-NSmut HCV vaccines will reduce 9-month incidence of chronic HCV infection compared to placebo among HCV-uninfected IDU.

The analysis of this objective will follow exactly the analyses described in Section 8.1 with the following modification:

- For subjects in the ATP (mITT) cohort without HCV infection, the 9-month chronic infection endpoint will be coded as censored, with time to event defined as the elapsed time from the second (first) vaccination, to the end of 26 month follow up, or to the last observed visit before loss to follow-up or of a criterion listed under the censoring criteria for the ATP (mITT) cohort.

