- For subjects in the ATP (mITT) cohort who develop HCV infection, the 9-month chronic infection endpoint will be coded as an observed event if the 9-month chronic infection endpoint definition is met, and as censored otherwise, with time to event defined as the elapsed time from the second (first) vaccination to the date of the sample collection with available test result nearest to the target assessment date of nine months after primary incident infection.

Kaplan-Meier curves will be presented in [Figure 7](#) and [Figure 8](#). Regression model summaries will be presented in [Table 14](#) and [Table 15](#).

Exploratory Objective 3: To determine if AdCh3NSmut1 and MVA-NSmut HCV vaccines will reduce peak concentration (magnitude) of HCV RNA compared to placebo, in blood samples of persons with incident HCV infection.

HCV RNA concentrations will be summarized by treatment group and by each month from HCV Infection for the ATP and mITT populations. Summaries will include n (number observed), minimum, maximum, geometric mean and the associated 95% confidence interval as well as geometric fold rise from the concentration at the first HCV RNA detection and the associated 95% confidence interval ([Table 16](#), [Table 17](#), [Table 18](#), [Table 19](#)). For each subject, the peak concentration from the first HCV RNA detection to the 6 month blood collection will be identified. The logarithmic peak concentrations will be compared between the vaccine and placebo groups using a two-sided t-test ([Table 20](#) and [Table 21](#)).

Exploratory Objective 4: To determine if AdCh3NSmut1 and MVA-NSmut HCV vaccines will reduce duration of HCV viremia (shorter time to spontaneous resolution) during incident infection (6-month period following incident HCV infection) compared to placebo in blood samples of persons with incident HCV infection.

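### SAP 8.3 censors HCV-negative completers at 26 months for the 9-month chronic endpoint, although its events run to about month 29 (latest Day 898), so the Kaplan-Meier tails in Figures 7 and 8 fall artificially

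*SAP*

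**What the plan says.** Protocol 11.4.3 sets the time for uninfected subjects in the 6-month analysis as running "to six months post completion of follow-up for acute HCV infection (26 months"). It then adds: "Time to event and censoring status for 9-month chronic infection are defined analogously".

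SAP 8.3, Exploratory Objective 2, says the analysis follows SAP 8.1 apart from two restated bullets. The bullet for infected subjects is updated: their time runs to the sample "nearest to the target assessment date of nine months after primary incident infection". The bullet for uninfected subjects is not: their time runs "from the second (first) vaccination, to the end of 26 month follow up, or to the last observed visit before loss to follow-up", the same figure that SAP 8.1 uses for the 6-month endpoint.

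Elsewhere the SAP recognises the longer horizon. Section 4.1 states: "Subjects who become viremic will be followed for 9 months after detection of HCV (up to month 29"). Section 3.3.2 requires, for this endpoint, "a subsequent sample collected at month 9 (not less than 249 or more than 291 days following incident infection"). SAP section 14, which lists departures from the protocol, does not mention a shorter censoring time for the 9-month endpoint.

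**The concern.** The two bullets no longer fit together. An infection first detected near the end of follow-up has its 9-month sample well after month 26. By then every HCV-negative completer has been censored, so the risk set holds only infected subjects waiting to be classified. Each late event is divided by a handful of people instead of about a hundred, and the Kaplan-Meier curve falls steeply.

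Figures 7 (ATP) and 8 (mITT) are planned report outputs. Taken at face value, their right-hand ends would say that most placebo subjects became chronically infected. The Cox results in Tables 14 and 15 are touched as well, because the late events are then compared among infected subjects only.

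**Working it through.** **Calendar.** The visit chart (Protocol Appendix C) equates month 20 with Day 600.

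- The plan's own figure: 20 + 6 = 26 months; 600 + 180 = Day 780. It reproduces.
- The analogous figure: 20 + 9 = 29 months; 600 + 270 = Day 870.
- Infections first detected at Visits 24, 25 and 26 (Days 540, 570, 600) have 9-month dates of Days 810, 840 and 870, all after Day 780.
- Latest possible event: Visit 26 has "Window: Day 593 to 607" (Protocol 8.2.15) and the sample window closes at 291 days, so 607 + 291 = Day 898.
- On the ATP clock, with dose 2 on Day 56, Days 780, 870 and 898 become 724, 814 and 842 days.

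**Simulation inputs.** 146 subjects per arm (292.5/2, SAP 5); 27 infections per 100 person-years (Protocol 11.4.5); chronic share 14/27, from the 14 per 100 person-years in SAP 5; a 60% vaccine effect, either by preventing infection (27 × 0.4 = 10.8 per 100 person-years) or by raising clearance (chronic share 5.6/27).

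**The mechanism by hand.** With dose 2 on Day 56, RNA visits on their nominal days, 9-month samples within ±7 days and no dropout (1,500 runs), the placebo curve stands at 0.845 at Day 780. About 7.8 infected subjects are still unclassified and about 4.1 of them will be events.

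- Completers kept at risk: about 105 subjects remain, so 0.845 × (1 − 4.1/105.4) = 0.812, an incidence of 19%.
- Completers removed: take 8 at risk, with 4 events falling when 8, 6, 4 and 2 remain. Then 7/8 × 5/6 × 3/4 × 1/2 = 0.273, and 0.845 × 0.273 = 0.23, an incidence of 77%. If the last subject at risk is an event, the curve reaches zero; this happened in 51% of placebo runs.

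**Fuller simulation.** Dose 2 on Days 49–63, RNA visits ±7 days, 9-month samples at detection + 270 days (±7 or ±21), no dropout; 300 trials per ATP scenario and 250 per mITT scenario. Ranges span the scenarios.

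| Cutoff for HCV-negative completers | Mean final incidence, placebo | Mean final incidence, vaccine |
|---|---|---|
| Day 780 | 81–84% | 43–75% |
| 780 days from dose 2 (about Day 836) | 74–76% | 34–56% |
| Day 870 | 33–54% (medians 20–24%) | 11–33% (medians 8–9%) |
| Day 898 | 19% | 8% |
| Any rule, read at about Day 760 | 15% | 6% |

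Under the Day 780 rule about 5–6 of about 36 events come after the last completer is censored, and the vaccine curve ends above 50% in 37–84% of runs. With an assumed 2% dropout per month the final figures are 72–76% and 40–60%, against about 18% and 8%.

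**Hazard ratio.** The SAP 8.1 model is stratified: "The stratification factors that will be used are gender and IL28B status". The stratum mix is an assumption (70% male, 40% CC). If the vaccine prevents infection, infected subjects in the two arms are equally likely to become chronic, so late events in infected-only risk sets pull the estimate toward 1: 0.37–0.40 becomes 0.39–0.43, a relative shift of 3–10%. If the vaccine only raises clearance, the comparison among infected subjects carries the same ratio and the estimate changes by no more than 0.01.

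**The case against.** The strongest reply is that little depends on this. The objective is exploratory. The report tabulates event counts, vaccine efficacy, a confidence interval and a p-value, but no final Kaplan-Meier estimate. The hazard ratio shift is at most about 0.15–0.2 of a standard error (standard error of the log hazard ratio about 0.38–0.40). Readers may discount a tail resting on a few subjects, and the figure shells, not visible here, might truncate the axis or print numbers at risk. All of this limits the importance. It does not make the curves right, and the SAP text specifies no truncation.

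Day 898 can also be disputed. Protocol 8.3.4 gives visit H09 a window of HCV Days 263–277, which makes the latest date 607 + 277 = Day 884. SAP 3.3.3 dates infection at an interval midpoint, which would be earlier still if the nine months ran from there. But the endpoint definition in SAP 3.3.2 counts from the first RNA-positive visit and accepts samples to 291 days, as do SAP 6.2 and the ±21 days in Protocol Appendix D. Day 898 covers every reading.

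Finally, by the same window standard the 6-month rule is slightly short: 607 + 201 = Day 808 against Day 780. That is true, but it leaves only about 0.3–0.5 events after the cutoff (median final incidence 20–22% and 8–9%). Its 20 + 6 months does match its own endpoint, so the primary rule is not part of this point.

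**Conclusion.** The point holds. The 26 months in SAP 8.3 Objective 2 was carried over from the 6-month endpoint; it conflicts with the protocol's analogous definition and with the SAP's own follow-up to month 29. The tails of Figures 7 and 8 would show a final incidence of roughly 80% on placebo and 43–75% on vaccine where 19% and 8% are right. The problem persists if the 26 months is counted from dose 2, and in part under a bare Day 870 cutoff. The curves before the cutoff are correct, and the effect on Tables 14 and 15 is small.

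The sizes are illustrative. They rest on the design rates, on no dropout in the main runs, and on at least one chronic case first detected near Visits 24–26. The rule should be corrected before the final analysis, but it does not threaten the trial's main conclusion.

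**What to change.** In SAP 8.3 Objective 2, replace the 26-month limit for HCV-negative completers with nine months after the end of infection follow-up (study month 29), carried through to the close of the 9-month sample window. For programming, state one cutoff per clock:

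- mITT: Day 898 from first vaccination.
- ATP: Day 898 minus the subject's own dose-2 day, measured from second vaccination (898 − 56 = 842 days after a Day 56 dose).

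Nominal month 29 (Day 870) should not be used as the cutoff, because it leaves a residual drop. State explicitly which vaccination the clock starts from. SAP 8.3 gives no time rule for the committee-determined 9-month analysis (Table 30); if that analysis uses the same rule, apply the same cutoff. Record the clarification in SAP section 14.

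The cost is one sentence in the SAP and the matching line of the programming specification. No extra data are needed.
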